If you indicated "Yes", please mark with an X next to each applicable category in the

column to the right and complete the remainder of this section

Prisoners					
Pregnant Women					
Cognitive impairment or emotional problems that potentially limit decision making					
Communication impairments that may preclude communicating a decision to discontinue participation or refuse participation					
Students of the investigator or investigator's department					
Employees of the investigator or investigator's department					
Children (minors)					
Terminally ill					
Other (specify):					
If you indicated any of the above, please justify your rationale for including these subjects.					
If you are using potentially vulnerable subjects as described above (infants, children, pregnant women/fetuses, terminally ill, decision-impaired, communication-impaired, students/employees, or prisoners), does the research create greater than minimal risk?	
 
 Yes	No	
 
 		
 
	Yes	No		
Yes	No				
					
If your subjects have a vulnerability that arises from their being students in your class or department, you will be asked for more information in Section 3.G. If the subjects have one of the other vulnerabilities, please describe proposed safeguards to protect vulnerable subjects.					
If not evident from the researcher qualification information in 1.D. or 1.E., please describe the researcher(s) qualifications for working with vulnerable subjects					

2.C. Study Design and Methodology

Part 1 – Purpose

Please briefly describe the **purpose** of your study. Note: Examples of study purposes are “to determine if a new reading intervention program improves 4th graders’ reading scores” or “to survey patients on their perception of physical therapy services”.

The primary purpose of this study is to develop pilot data that will be used to demonstrate the feasibility of a larger study for which we will plan to seek external funding. We will compare the performance of study participants’ on several neuropsychological measures as well as their rate of learning on a computer-delivered working memory task in groups randomly assigned to receive either sham or true tDCS.

Part 2 – Goals and Justification

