Participants receiving **active tDCS** will then receive 1.5 mA tDCS delivered by the Chattanooga Ionto electrophoresis device for 20 minutes while completing working memory training with the Brain Workshop software (example computer screens are included in the Appendix). The device provides an initial 30 s ramp-up of current so as to minimize discomfort and is designed to deliver a constant current even in the face of possible fluctuations in impedance due to changes in electrode or skin characteristics (e.g., increased resistance as the electrode dries). It includes circuitry that continuously monitors impedance so that if it changes beyond safety parameters the device immediately shut off with an audio alarm. This provision reduces risk of participant discomfort or other negative effects. The device also is controlled with a timer that guarantees a specific dose tDCS; it automatically ramps down the current and shuts off at the end of the session (20 minutes).

Participants receiving **sham tDCS** will be treated in the same fashion (fitted with the electrodes and headband) but current will be provided only for the 30 sec ramp up period and five seconds after that, when the current will ramp down. This provides no tDCS-related effect but provides the participant with a stimulus that is discernible by most persons. Since many persons only perceive the current at the beginning of a stimulation session (even when it continues for 20 minutes) this is believed to be an adequate control and is a strategy has been used in multiple other studies.

As the device does not provide for double-blinding in the delivery of tDCS (i.e., the operator must program it and will know if the person receives active or sham stimulation), [name] will plan

to sit to one side and behind the participant in order to monitor the participant, encourage his work on the cognitive training task, provide tutoring on the task and interacting with the computer as needed. The study is thus single blind, and we will assess the success of blinding by asking participants which group they were in as part of the final study visit.

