Cognitive Training. During the study visit, both groups will be asked to work with the n-back training program Brain Workshop. The phrase “n-back” refers to the task’s requirement to monitor a series of discrete events (either blue blocks flashing on the screen in one of 9 positions or a series of letter heard over audio) and remember one that occurred a specific number prior to the current one. The number of prior events monitored is the “n.” The participant is asked to press a letter on a keyboard when the current stimulus matches one delivered “n” times previously. For example, for a 2-back task using the letter series “a – d – g – d,” the participant would respond with a key press when hearing the second letter “d” as it matches a letter presented two instances before the current one.

As this task can be challenging for those with cognitive impairments and we have previous experience in using it with older persons, the task’s difficulty is tailored to individuals’ abilities and can be increased as the participant shows greater levels of performance over time. Participants’ performance is tracked automatically by the software and will be recorded only with the participant’s research number.

At the conclusion of this visit and all subsequent visits, participants will provide brief ratings of their cognitive function, mood, and level of discomfort (see Appendix for questions).

Randomization: Participants will be randomized to treatment condition in permuted blocks of four, with a plan to recruit six blocks of four (total participants 24) based on power analyses that suggest a sample size of 12 in each group provides a power of 0.80 to detect between group differences. As we wish to obtain a final sample size of 12 in each group, however, depending on drop outs or persons otherwise lost to follow-up, we will plan to recruit two additional blocks of 4 up to a total number of 32 participants. The planned enrollment table in section 2A of this protocol thus indicates a possible total enrollment of 32.

5) Subsequent study visits. Participants will complete a total of six 20-minute training sessions with sham or true tDCS and working memory training. Participants will be asked to complete three sessions per week, and must complete all training sessions within three weeks.

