Risk Minimization	Several participants in previous studies of tDCS for depression developed manic or hypomanic episodes. In the largest and best controlled study (Brunoni et al., 2013), the occurrence of these episodes was similar in groups receiving only antidepressant medication and in those receiving antidepressant medication plus tDCS. Since some persons who appear to have unipolar depression may actually have unrecognized bipolar disorder, the significance of this finding for risk in studies of tDCS for cognitive problems is not clear. In order to minimize this risk, however, we will screen persons for a history of mania or hypomania as well as for a personal or family history of bipolar disorder. We will also exclude anyone taking mood stabilizing medication (anticonvulsants or lithium; see list in exclusion criteria) as patients are sometimes given mood stabilizers for possible mood disorders without a clear understanding of the purpose of these medications.
Risk/Discomfort	Distress, frustration, or fatigue from the difficulty of the computer-delivered cognitive training task
Likelihood	Low
Magnitude/Duration	Mild/throughout the study
Risk Minimization	Participants will be closely monitored during training sessions and provided ongoing coaching and encouragement to help them become proficient at the memory and attention task and to not become excessively frustrated. The task itself is designed to begin with a low level of difficulty and progress so as to continuously challenge the participant without becoming excessively difficult. We have already completed preliminary acceptability testing of the cognitive training activity with a group of HIV+ participants who are similar to those to be enrolled in the proposed study ("Usability of Revised Educational and Cognitive Training Interventions for HIV," Protocol No. 05251228Exp)

	and found a high level of acceptance for it.
Risk/Discomfort	Inadvertent disclosure of HIV status or other information that might be embarrassing to the participant.
Likelihood	Low.
Magnitude/Duration	Large/throughout the study

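### Task help given by an operator who knows the arm is not standardised, and the protocol does not say who gives or scores the final test battery

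*Protocol*

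**What the plan says.** **Who knows the arm.** Protocol section 2.C Part 3, step 4, explains that the stimulator cannot be run double-blind because "the operator must program it and will know if the person receives active or sham stimulation". The same sentence gives this as the reason why a person (name removed) will sit beside and behind the participant, monitor, and "encourage his work on the cognitive training task, provide tutoring on the task and interacting with the computer as needed". The protocol then calls the study single blind. Its only planned check of blinding is the participant's own guess at the final visit.

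**Help with the task.** Section 3.K, in the entry on frustration with the training task, says participants will be "provided ongoing coaching and encouragement to help them become proficient at the memory and attention task". It continues: "The task itself is designed to begin with a low level of difficulty and progress so as to continuously challenge the participant". The Cognitive Training paragraph in 2.C Part 3 says difficulty is fitted to the individual and can be raised, without saying by whom. It also says "performance is tracked automatically by the software".

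**The task as an outcome.** Section 2.C Part 1 (Purpose) compares participants' "rate of learning on a computer-delivered working memory task in groups randomly assigned to receive either sham or true tDCS". Section 3.M and the SAP list the learning rate as an additional outcome, with slopes plotted and formally tested.

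**Equal treatment.** Sham participants "will be treated in the same fashion (fitted with the electrodes and headband"; the parenthesis covers only the fitting. Section 3.P requires an investigator in sham sessions as well as active ones.

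**Final battery.** Step 6 repeats the screening tests and also collects the arm guess. It names neither tester nor scorer. At the eligibility visit (step 3), before randomisation, the researcher scores them.

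**The concern.** A training outcome is open to bias when the person helping with the task knows the arm and decides how much help to give. Blinding the participant does not close that route, because the bias comes from what the helper does and not from what the participant believes.

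The direction is not fixed. If the helper expects active stimulation to work and coaches that arm more, the slope difference would look like a tDCS benefit. If help follows need and sham participants learn more slowly, they would get more help and a true difference would shrink.

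The final battery raises a second, separate question. It supplies the neuropsychological outcomes named first in section 3.M and the SAP. Its tests are timed, prompted or scored by an examiner, so knowing the arm could affect either administration or scoring.

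The stated aim is pilot data to support a larger, externally funded study. A distorted estimate in either direction would carry into that study's design.

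**Working it through.** **Step 1. Is the helper the person who knows the arm?** The name is removed, so this is an inference. One sentence gives the operator's knowledge of the arm as its reason and the seating and tutoring arrangement as its consequence. The natural reading is that operator and tutor are the same person. Sitting behind the participant may limit visual cues but does not govern the amount of help.

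**Step 2. Does anything supplied equalise the help?**
- Automatic tracking protects the recording of the score, not the performance being recorded.
- Section 3.K suggests difficulty progresses by design, while the Cognitive Training paragraph leaves open who raises it.
- The same-fashion wording for sham is spelled out only as electrodes and headband.
- Coaching in 3.K is offered without distinction by arm, and 3.P puts an investigator in sham sessions. Both concern availability and presence, not amount or content.

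No supplied text gives a script or a limit for help.

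**Step 3. Can the analysis repair it?** Section 3.M and the SAP adjust the neuropsychological comparison for age, CD4 count, mood and baseline score. These are baseline variables and cannot remove a bias that arises during training or final testing. No covariates are attached to the learning slopes.

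**Step 4. The plan's own figure.** Section 2.C Part 3 (Randomization) says power analyses suggest that "a sample size of 12 in each group provides a power of 0.80 to detect between group differences". It gives no alpha, sidedness, effect size or SD, so this cannot be reproduced. Solving backwards with a two-sample t-test and an assumed two-sided alpha of 0.05 gives a detectable difference of about 1.20 SD.

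**Step 5. Scale of a bias, for illustration.**
- Inputs: n = 12 per arm (protocol); two-sided alpha 0.05 (assumed); no true effect; a pure bias of d SD between arms (assumed, since the documents give none).
- Formula: the test statistic is noncentral t with 2n − 2 = 22 degrees of freedom and noncentrality d × √(n/2) = d × √6. Rejection is the probability that it falls outside ± the central-t critical value.

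| Assumed bias d (SD) | d × √6 | Probability of rejection |
|---|---|---|
| 0 | 0 | 5.0% |
| 0.2 | 0.49 | 7.6% |
| 0.3 | 0.73 | 10.8% |
| 0.5 | 1.22 | 21.6% |

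These are unadjusted rates. They show what a bias of a given size would do, not that this trial has one.

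**The case against.** The strongest reply has four parts.

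**The protocol is open about the limitation.** It attributes unblinded operation to the device and claims only single blinding, and the study is a pilot whose primary purpose is feasibility data. This stands as context. It does not answer the point, because the amount of help and the masking of scorers do not depend on the device.

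**Exposure is limited.** The learning rate is an additional outcome scored by software. The depression scale and the functioning questionnaire are completed by participants who are meant to be blind. This stands and limits the severity, although the Purpose section also names learning rate as a comparison.

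**Help is a safeguard.** Coaching is the protocol's own measure against frustration, on a task it describes as challenging for people with cognitive impairment. This stands: any script has to be reconciled with section 3.K.

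**The part about the final battery argues from silence.** The final-visit flow sheet sits in an appendix that was not supplied, and some pages were removed from the copy reviewed. Masked testing may be described there. This stands, so the supportable claim is that the supplied text does not say who tests and scores.

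Two stronger readings are tempting. A reader might infer that the arms will be coached differently, or that any tDCS effect found would be spurious. The documents show only that unequal help is possible, and help given according to need is not in itself operator bias. A reader might also infer from section 3.K (burns) that two staff attend each visit, so that a second tester is at hand. That entry joins two removed names with *or*, which guarantees only one person.

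**Conclusion.** The concern holds in a limited form. As written, the plan lets a person who, on the natural reading, knows the arm decide how much help each participant gets on a task whose learning rate is compared between arms. That could bias the slopes towards or away from a tDCS benefit, and baseline adjustment would not remove it. The supplied text also leaves the tester and scorer of the final battery unstated.

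The size is unknown. The rejection rates of 7.6%, 10.8% and 21.6% rest on an assumed bias, an assumed alpha and no true effect, and the finding does not depend on them. It rests on two conditions: that operator and tutor are the same person, and that the material not supplied does not already provide for standardised help and masked testing. The point should be settled before enrolment. It does not invalidate the design.

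**What to change.** 1. **Standardise task help.** Use one written script for instructions, help and encouragement in both arms. Reconcile it with the coaching measure in section 3.K so that support stays equally available. State whether the software or staff set n-back difficulty, and apply the same rule in both arms.
2. **Mask the scoring.** Have the final-visit test sheets scored by a team member who has not seen the allocation. Section 3.K already provides for sheets coded by number; keep the arm off them. Ask for the participant's arm guess only after the battery.
3. **Separate the tester where existing staffing allows.** Have the battery given by someone who did not operate the device for that participant. Otherwise, state that masked scoring does not remove bias in administration, timing or prompting. A second person should not be assumed.

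If the flow sheet already provides for masked testing, one sentence in the protocol would settle that part.

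A tally of prompts by arm may look like a natural check, but it is not recommended as a test for bias. Help follows performance after randomisation, so a difference between arms could not separate operator bias from need, and the unblinded tutor would probably be the one keeping the tally.

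Cost: a short script, somewhat less tailored help, and some scheduling. Items 1 and 2 leave sample size, number of visits, randomisation and stimulation unchanged. Item 3 may need extra staff, which is why it is conditional.

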Participants who continue to meet all study criteria with respect to medical history and medication use (see flow sheet) will complete four brief neuropsychological measures (Hopkins Verbal Learning Test; Trail Making Test Parts A and B; Wechsler Adult Intelligence Scale Digit Span subtest; Grooved Pegboard; all listed below) as well as complete the Center for Epidemiological Studies Depression and the Patient's Own Assessment of Functioning Scale. These will take approximately 45 minutes to complete. After completing these measures, they will be provided with a break (approximately 5-10 minutes) while the researcher scores the measures and determines the potential participant's eligibility given the evidence of both subjective cognitive complaints and objectively below average (at least 1 standard deviation below normative performance) on at least two of the measures. If participants are not eligible based on their cognitive performance, they will be thanked for their attendance, asked if they have any questions, and provided compensation.

Participants who show evidence of below average cognitive performance in two areas assessed will be informed that they are eligible to participate in the study. Their continued interest in participation will again be elicited, and if they continue to state they would like to participate, the investigator will review the written informed consent form with the potential participant, answer questions about the study, and provide the potential participant with sufficient time to review the written informed consent form. The investigator will then ask the participant to briefly recount the purpose of the study as well as its risks and benefits using a previously validated procedure

(Palmer et al., 2005). If participants cannot provide adequate answers to these questions, the person obtaining informed consent will review the material until they achieve a satisfactory performance defined as a score of 4 out of a possible 6 on the three questions (see visit flow sheet for questions and scoring criteria).

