Cognitive Training with and without tDCS to Improve Cognition in HIV

December 2, 2014

Statistical Analysis Plan

Study outcomes will be evaluated through analysis of group differences on neuropsychological measures after correction for baseline differences in age, disease status (CD4 count), mood, and baseline performance. Additional outcomes will include the rate of learning in the computer-delivered memory and attention task between groups. Individual and group slopes for the task will be plotted and visually inspected as well as tested using parametric statistics.

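### Does the protocol's 0.80 power at 12 per group need restating, given that no effect size, alpha or endpoint is attached to it?

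*Protocol*

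**What the plan says.** The sample size rests on one sentence in the Randomization paragraph of protocol section 2.C, Part 3, step 4: power analyses indicated that "a sample size of 12 in each group provides a power of 0.80 to detect between group differences". The plan is six blocks of four, 24 participants. To keep 12 per group despite losses, "we will plan to recruit two additional blocks of 4 up to a total number of 32 participants". The phrase "to detect between group differences" carries no size, and the inputs of the power analyses are not given.

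The SAP, whose wording repeats protocol section 3.M, plans to assess "group differences on neuropsychological measures after correction for baseline differences in age, disease status (CD4 count), mood, and baseline performance", with the learning rate on the computer task as an additional outcome. Neither text names a primary outcome or an alpha. Protocol section 2.C, Part 1 gives the main purpose as "to develop pilot data that will be used to demonstrate the feasibility of a larger study".

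**The concern.** A power is a property of a particular difference, test and alpha. Stated bare, 0.80 invites the reader to think the trial will probably find whatever effect exists. Under ordinary assumptions, 12 per group reaches 0.80 only for a large difference, and both arms receive the same training, so the contrast is only what stimulation adds. Several scores will be compared, which would lower the power further if the tests were corrected for multiplicity.

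What would be at stake is the next trial. If the pilot were taken as adequately powered, a null result could be read as evidence against tDCS although the interval excludes little. A significant estimate from so small a sample could overstate a moderate true effect and lead to an undersized successor.

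**Working it through.** **Inputs from the documents.** 12 per group, two arms, power 0.80 (protocol 2.C, Part 3, step 4); four covariates: age, CD4 count, mood and baseline performance (SAP).

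**Inputs assumed, because the documents give none.** Two-sided alpha 0.05; one endpoint; outcome SD of 1, so differences are in SD units; multiple correlation R of the covariates with the outcome, varied from 0.3 to 0.8.

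**1. Reproducing the stated figure.** It cannot be reproduced from documented inputs. It can only be inverted to find the difference d at which it would be true.

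**2. Unadjusted two-sample t-test.** Degrees of freedom 12 + 12 − 2 = 22, critical t = 2.074, standard error √(2/12) = 0.408, noncentrality d/0.408. Noncentral t gives:

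| d (SD) | power |
|---|---|
| 0.5 | 0.22 |
| 0.8 | 0.47 |
| 1.0 | 0.65 |
| 1.2 | 0.80 |

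The exact solution for 0.80 is d = 1.197, or 1.05 if the test is one-sided at 0.05. The 95% interval half-width is 2.074 × 0.408 = 0.85 SD, which is also the smallest observed difference that reaches significance.

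**3. The planned adjusted model.** Group plus four covariates leaves 24 − 2 − 4 = 18 degrees of freedom. Chance covariate imbalance inflates the variance of the group contrast by about 1 + 4/(24 − 4 − 3) = 1 + 4/17 = 1.235. The detectable difference is 1.21 residual SD from the degrees of freedom alone, and 1.21 × √1.235 = 1.34 residual SD with the inflation. Multiplying by √(1 − R²) converts to raw SD:

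| assumed R | detectable difference (raw SD) | power at 0.5 SD |
|---|---|---|
| 0.3 | 1.28 | 0.19 |
| 0.5 | 1.16 | 0.23 |
| 0.7 | 0.96 | 0.31 |
| 0.8 | 0.81 | 0.41 |

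The 1.34 and the 1.20 are in different units and should not be compared directly. In raw SD, adjustment beats the unadjusted 1.20 at the R values of 0.5 and above.

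**4. Significance threshold under the planned model.** 2.101 × 0.408 × √1.235 × √(1 − R²) is about 0.68 SD at R = 0.7 and 0.57 at R = 0.8. The 0.85 in step 2 therefore belongs to a test the SAP does not plan. The same holds for the exaggeration of significant results when the true d is 0.5: by simulation, about 2.1-fold for the unadjusted mean difference (2.2-fold in sample-SD units).

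**5. Multiplicity.** Bonferroni over five scores would raise the unadjusted detectable difference to 1.51 SD and cut power at 1.2 SD to 0.56. The five is an inference: protocol 2.C, Part 3, step 3 lists four measures, and nothing says the two Trail Making parts are tested separately or that Bonferroni will be used.

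**6. Comparison with the entry criterion.** Eligibility requires performance "objectively below average (at least 1 standard deviation below normative performance) on at least two of the measures". That is a floor in normative SDs. The detectable difference is in trial-sample SDs, which the documents do not give. The two cannot be set equal.

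**The case for a change.** The strongest case for a change is that this sentence is the sole numerical basis for 24 participants, cannot be checked, and could be repaired in two or three sentences before data are seen, with no extra patients. The arithmetic behind it is sound: even with covariates at R = 0.8, power at 0.5 SD is only 0.41. The figure may also accompany the pilot data into a funding application.

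What stands is that the sentence is incomplete and must not be quoted as the power for effects in general. What does not stand is the step to an error. No documented input is inconsistent with 0.80; the investigators may have assumed a large effect, a one-sided test or strongly prognostic covariates. Writing 1.2 SD, 47% and 22% into the protocol would replace their power analyses with back-solved values from an unadjusted test they do not plan to run. Misreading is possible, but no document sets a significance-based decision rule or says the larger trial will be sized from a significant point estimate.

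**Conclusion.** No change to the plan is needed. The power statement omits its inputs, so it is unverifiable rather than shown to be wrong. On one endpoint it corresponds to about 1.20 SD for an unadjusted two-sided 0.05 test, or to 1.28 down to 0.81 raw SD for the planned adjusted model with R assumed between 0.3 and 0.8. Those values rest on the assumed alpha, sidedness and R.

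Filling the gap would not alter who is randomised, how many, which model is fitted or what is estimated. For a declared pilot, an analyst would ordinarily report the adjusted difference with its 95% interval, and that interval shows how little 24 participants can settle more plainly than a revised power sentence would. A reader using these data to plan the larger trial should work from the interval and disregard the bare 0.80.
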